#### Laboratory test interactions

False elevations of urinary catecholamine levels may occur due to interference with the fluorescence test.

#### Effects on ability to drive and use machines

The effect of doxycycline on the ability to drive or operate heavy machinery has not been studied. There is no evidence to suggest that doxycycline may affect these abilities.

#### Undesirable effects

The following adverse reactions have been observed in patients receiving tetracyclines, including doxycycline.

**Autonomic nervous system.** Flushing.

**Body as a whole.** Hypersensitivity reactions, including anaphylactic shock, anaphylaxis, anaphylactoid reaction, anaphylactoid purpura, hypotension, pericarditis, angioneurotic oedema, exacerbation of systemic lupus erythematosus, dyspnoea, serum sickness, peripheral oedema, tachycardia and urticaria.

**Central and Peripheral nervous system.** Headache. Bulging fontanelles in infants and benign intracranial hypertension in juveniles and adults have been reported in individuals receiving full therapeutic dosages of tetracyclines. In relation to benign intracranial hypertension, symptoms included blurring of vision, scotomata and diplopia. Permanent visual loss has been reported.

**Gastro-intestinal.** Gastro-intestinal symptoms are usually mild and seldom necessitate discontinuation of treatment. Abdominal pain, anorexia, nausea, vomiting, diarrhoea, dyspepsia and rarely dysphagia. Oesophagitis and oesophageal ulceration have been reported in patients receiving Vibramycin. A significant proportion of these occurred with the hyclate salt in the capsule form.

**Hearing/Vestibular.** Tinnitus.

**Haematopoietic.** Haemolytic anaemia, thrombocytopenia, neutropenia, porphyria, and eosinophilia have been reported with tetracyclines.

**Liver/Biliary.** Transient increases in liver function tests, hepatitis, jaundice, hepatic failure and pancreatitis have been reported rarely.

**Musculo-Skeletal.** Arthralgia and myalgia.

**Skin.** Rashes including maculopapular and erythematous rashes, exfoliative dermatitis, erythema multiforme, Steven-Johnson syndrome and toxic epidermal necrolysis. Photosensitivity skin reactions.

**Superinfection.** As with all antibiotics, overgrowth of non-susceptible organisms may cause candidiasis, glossitis, staphylococcal enterocolitis, pseudomembranous colitis (with *Clostridium difficile* overgrowth) and inflammatory lesions (with candidal overgrowth) in the anogenital region. Similarly there have been reports for products in the tetracycline class of stomatitis and vaginitis.

**Urinary system.** Increased blood urea.

**Other.** When given over prolonged periods, tetracyclines have been reported to produce brown-black microscopic discolouration of thyroid tissue. No abnormalities of thyroid function are known to occur.

Tetracyclines may cause discoloration of teeth and enamel hypoplasia, but usually only after long-term use.

### Overdose

Acute overdosage with antibiotics is rare. In the event of overdosage discontinue medication. Gastric lavage plus appropriate supportive treatment is indicated. Dialysis does not alter serum half-life and thus would not be of benefit in treating cases of overdosage.

### Pharmacodynamic properties

Vibramycin is primarily bacteriostatic and is believed to exert its antimicrobial effect by the inhibition of protein synthesis. Vibramycin is active against a wide range of Gram-positive and Gram-negative bacteria and certain other micro-organisms.

### Pharmacokinetic properties

Tetracyclines are readily absorbed and are bound to plasma proteins in varying degrees. They are concentrated by the liver in the bile and excreted in the urine and faeces at high concentrations and in a biologically active form. Doxycycline is virtually completely absorbed after oral administration. Studies reported to date indicate that the absorption of doxycycline, unlike certain other tetracyclines, is not notably influenced by the ingestion of food or milk. Following a 200mg dose, normal adult volunteers averaged peak serum levels of 2.6 micrograms/ml of doxycycline at 2 hours decreasing to 1.45 micrograms/ml at 24 hours. Doxycycline has a high degree of lipid solubility and a low affinity for calcium. It is highly stable in normal human serum. Doxycycline will not degrade into an epianhydro form.

### List of excipients

Vibramycin 50mg capsules: Maize Starch Ph.Eur., Lactose Ph.Eur., alginic acid, Magnesium Stearate NF, Sodium Lauryl Sulphate Ph Eur. In addition the capsule shell cap contains: Gelatin BP, titanium dioxide (E171), patent blue V (E131) and quinoline yellow (E104) and the body contains yellow iron oxide (E172), indigotine (E132) and titanium dioxide (E171).

Vibramycin D Dispersible tablets: Anhydrous Colloidal Silica Ph.Eur., Microcrystalline Cellulose Ph.Eur. and Magnesium Stearate Ph.Eur.

### Shelf life

Vibramycin 50mg capsules 48 months.

Vibramycin D Dispersible tablets 48 months.

Store below 25°C.

### **Drug interactions**

- Because tetracyclines have been shown to depress plasma prothrombin activity, patients who are on anticoagulant therapy may require downward adjustment of their anticoagulant dosage.
- Since bacteriostatic drugs may interfere with the bactericidal action of penicillin, it is advisable to avoid giving tetracyclines in conjunction with penicillin.
- Absorption of tetracyclines is impaired by antacids containing aluminum, calcium, or magnesium, and iron-containing preparations.
- Absorption of tetracycline is impaired by bismuth subsalicylate.
- Barbiturates, carbamazepine, and phenytoin decrease the half-life of doxycycline.
- The concurrent use of tetracycline and Penthrane (methoxyflurane) has been reported to result in fatal renal toxicity.
- Concurrent use of tetracycline may render oral contraceptives less effective.

### **Toxicity and interruption or discontinuation of treatment**

Toxicity will be assessed by the National Cancer Institute's Common Terminology Criteria for Adverse Events v3.0 (CTCAE) (copy attached) (also available on <http://ctep.cancer.gov/forms/CTCAEv3.pdf>).

### **Expected adverse events related to doxycycline**

Doxycycline is a widely used antibiotic for which serious side effects are rare. The drug is absorbed by the oral route and eliminated with a half-life of 18 hours, by faecal and renal excretion. Absorption is not significantly affected by the presence of food in the stomach. Doxycycline does not accumulate significantly in patients with renal function impairment. In the blood, doxycycline is 90 % protein-bound. The usual adult therapeutic dose is 100 to 200 mg/day.

#### Frequent adverse effects:

- Anorexia, nausea, vomiting, heart burn.
- Photosensitivity reactions upon exposure to direct sunlight, erythema or skin rashes. Skin and nail hyperpigmentation.
- Discoloration of teeth.
- Diarrhoea.

In addition a larger number of infrequent side effects have been reported.

**Hematological.** Haemolytic anaemia, thrombocytopenia, neutropenia and eosinophilia have all been reported (116-118). Elevation of pro-thrombin times can occur and for this reason those patients taking warfarin will be excluded from the study.

**Central nervous system effects.** Benign intracranial hypertension has been associated with doxycycline use which resolved when treatment was stopped. (119,120).

**Endocrine/metabolic.** Rare cases hypoglycaemia and lactic acidosis have been reported (121-123).

**Gastrointestinal:** Drug-induced oesophagitis occurs in about four percent of the population taking oral doxycycline (124). This can be avoided by increasing water intake when swallowing the capsules. Nausea, vomiting, anorexia, diarrhoea, glossitis and enterocolitis have also been reported. (125-139). Symptoms are often self-limiting. Antacids or sucralfate (136) will resolve most ulcers in several days to a week. Rarely, symptoms have lasted as long as 4 weeks after therapeutic intervention. Ulcers are more often associated with capsules than tablets, especially capsules that do not contain the enteric-coated formulation. Doxycycline should be taken with a full glass of water and the patient should remain in the upright position for at least thirty minutes. Preferably, it should be taken with food and not before going to sleep.

**Renal.** Doxycycline can be used safely in patients with renal disease as the drug can be eliminated almost completely through the gastrointestinal tract. Doxycycline may reduce the efficacy of oral contraceptives. Patients taking the oral contraceptive pill will be excluded from the study.

**Skin:** Photosensitivity reactions have been reported in about 8 to 11% of patients taking doxycycline (141-151). Patients will be advised to avoid direct sunlight and use sunscreens. Doxycycline should be discontinued if erythema occurs. Stevens-Johnson syndrome has been reported in three patients (152-154).

**Alterations in gut microflora.** Doxycycline in doses of 100 mg daily causes only moderate changes (suppression) in oropharyngeal and colonic microflora (155,156). Like other antibiotics, *Clostridium difficile* has been reported in some patients (157). In three studies, 40 mg / day of Doxycycline did not effect the composition or resistance of fecal or vaginal microflora over 9-months (158). Nor was there a difference in the number of side effects between patients treated with doxycycline or placebo for 9 months, (159).

**Hypersensitivity.** Hypersensitivity reactions including urticaria, angioneurotic oedema, anaphylaxis, purpura, and serum sickness are very rare (162,163).

**Tooth discoloration.** Permanent discoloration of the teeth has been associated with tetracyclines. This is most common in children under 8 (no children will be recruited to the study). Reversible tooth discoloration can occur in adults in short but more commonly long-term treatment (164).

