### Statistical analysis of endpoints

#### Primary endpoint

The primary endpoint will be the difference in rate of decline of FEV1 (ml/year) measured over 24 months.

All data will be analysed on an intention to treat basis in conjunction with the trial statistician [name]. The mean slope of regression lines for FEV1 and FVC, plus change in DLCO, shuttle walk distance and quality of life in the doxycycline and placebo groups will be compared by parametric or non-parametric analysis as appropriate following analysis of the data for normality. In addition we will perform a *per protocol* analysis of mean rate of change of FEV1/year. Time to composite safety endpoint will be analysed by Kaplan-Meier analysis, complications and adverse events by Chi Square test. Patients withdrawing from the study will continue to have measurements made where possible for intention to treat analysis. Missing values will be handled by multiple imputation.

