### Special warnings and precautions for use

**Use in patients with impaired hepatic function** Vibramycin should be administered with caution to patients with hepatic impairment or those receiving potentially hepatotoxic drugs.

Abnormal hepatic function has been reported rarely and has been caused by both the oral and parenteral administration of tetracyclines, including doxycycline.

**Use in patients with renal impairment.** Excretion of doxycycline by the kidney is about 40%/72 hours in individuals with normal renal function. This percentage excretion may fall to a range as low as 1-5%/72 hours in individuals with severe renal insufficiency

(creatinine clearance below 10ml/min). Studies have shown no significant difference in the serum half-life of doxycycline in individuals with normal and severely impaired renal function. Haemodialysis does not alter the serum half-life of doxycycline. The anti-anabolic action of the tetracyclines may cause an increase in blood urea. Studies to date indicate that this anti-anabolic effect does not occur with the use of Vibramycin in patients with impaired renal function.

**Photosensitivity.** Photosensitivity manifested by an exaggerated sunburn reaction has been observed in some individuals taking tetracyclines, including doxycycline. Patients likely to be exposed to direct sunlight or ultraviolet light should be advised that this reaction can occur with tetracycline drugs and treatment should be discontinued at the first evidence of skin erythema.

**Microbiological overgrowth** The use of antibiotics may occasionally result in the overgrowth of non-susceptible organisms including Candida. If a resistant organism appears, the antibiotic should be discontinued and appropriate therapy instituted.

Pseudomembranous colitis has been reported with nearly all antibacterial agents, including doxycycline, and has ranged in severity from mild to life-threatening. It is important to consider this diagnosis in patients who present with diarrhoea subsequent to the administration of antibacterial agents.

**Oesophagitis** Instances of oesophagitis and oesophageal ulcerations have been reported in patients receiving capsule and tablet forms of drugs in the tetracycline class, including doxycycline. Most of these patients took medications immediately before going to bed or with inadequate amounts of fluid.

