#### Management of adverse events associated with doxycycline

**Gastrointestinal.** To reduce the risk of oesophagitis enteric-coated capsules will be used and patients will be advised to take doxycycline at meal times with a full glass of water. If these measures are unsuccessful, we will withdraw the drug and ask the patient to be evaluated by a gastroenterologist.

**Cutaneous.** Patients will be advised about the risk of photosensitivity, and to use good sun protection. For patients in whom a significant episode of tetracycline-induced

photosensitivity develops, treatment with doxycycline will be interrupted for a week to allow resolution of the skin reaction. Methods to protect the skin from exposure to light will be discussed with the patient, and doxycycline treatment will be resumed at the same dose. If this is unsuccessful in preventing further photosensitivity reactions, patients will be withdrawn from the study.

**Dental.** For patients in whom tooth discoloration develops, vigorous oral hygiene will be advised, along with regular follow-up with a dental technician for formal cleansing. Patients will be advised not to use chlorhexidine-containing mouthwashes, which can cause tooth discoloration. If this is unsuccessful in resolving tooth discoloration to the patient's satisfaction, the patient will be removed from the study.

**Infectious.** Doxycycline may cause moderate changes in oropharyngeal and colonic microflora. Non-antimicrobial doses of doxycycline do not appear to have an effect on the composition or resistance of faecal or vaginal microflora (167). It is possible that patients may become colonized with doxycycline resistant organisms. For patients in whom any form of yeast infection developed during the course of the study, doxycycline treatment may be interrupted to permit resolution of the infection, along with vigorous hygiene and anti-fungal treatment, followed by resumption of the study medication.

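### The protocol gives two different study-drug instructions for photosensitivity (discontinue at erythema; or interrupt for a week and resume) and does not say which governs

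*Protocol*

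**What the plan says.** Section 6 of the protocol deals with skin reactions in three places.

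- **Special warnings and precautions for use**, photosensitivity entry: "treatment should be discontinued at the first evidence of skin erythema".
- **Frequent adverse effects**, skin entry: "Photosensitivity reactions have been reported in about 8 to 11% of patients taking doxycycline", followed by advice on sun avoidance and sunscreen, and then "Doxycycline should be discontinued if erythema occurs".
- **Management of adverse events associated with doxycycline**, cutaneous paragraph. The trigger is worded "For patients in whom a significant episode of tetracycline-induced" photosensitivity. The action is that "treatment with doxycycline will be interrupted for a week to allow resolution of the skin reaction", after which light protection is discussed "and doxycycline treatment will be resumed at the same dose". Withdrawal from the study follows only if this fails to prevent further reactions.

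On follow-up, the primary endpoint text under Statistical analysis of endpoints (section 4) says "Patients withdrawing from the study will continue to have measurements made where possible for intention to treat analysis". It also specifies intention to treat, multiple imputation for missing values, and an additional per-protocol analysis of the FEV1 rate of change.

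**The concern.** An investigator who sees a patient with a significant erythematous reaction finds two instructions. One stops doxycycline and mentions no restart. The other pauses it for a week and restarts it at the same dose. A patient with slight erythema meets the first instruction but arguably not the second, because the management paragraph applies only to a significant episode and does not define that word.

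Two things are at stake. The first is safety and consistency: two patients with the same reaction could be handled differently, each in line with some part of the protocol. The second is the analysis. Whether a patient pauses briefly or stops alters time on treatment, and possibly whether she counts in the per-protocol FEV1 analysis. With 20 patients planned per arm, each is 5% of the arm (1/20).

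**Working it through.** **1. The statements side by side**

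| | Frequent adverse effects (echoed in Special warnings) | Management of adverse events |
|---|---|---|
| Trigger | Any erythema (Special warnings: its first sign) | A significant photosensitivity episode; term not defined there |
| Action | Discontinue | Interrupt for one week |
| Return to drug | Not mentioned | Yes, same dose |
| Withdrawal | Not mentioned | Only if further reactions are not prevented |

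The protocol appears to treat interruption and discontinuation as different things. The heading that opens its toxicity text names both as alternatives, and the management paragraph uses separate words for pausing and for withdrawing. No sentence ranks one statement above the other.

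**2. Number of patients exposed**

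The plan is for 40 patients (Patient population and recruitment) randomised 1:1 (Randomisation), so 20 on doxycycline. This agrees with the Sample size section: a 70 ml/year difference, SD 75 ml/year and 80% power. With two-sided alpha 0.05 (the level is stated for the FVC test; two-sided is assumed):

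n per group = 2 × (1.960 + 0.842)² × (75/70)² ≈ 18.02, rounded up to 19, against 20 stated.

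Power at 20 per group is 0.84 by the normal approximation and 0.82 by the t-test. The figure of 20 is sound as the basis for what follows.

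**3. How often a reaction would occur**

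The rate is 8 to 11% (skin entry, Frequent adverse effects).

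- Expected cases: 20 × 0.08 = 1.6; 20 × 0.11 = 2.2.
- At least one: 1 − 0.92²⁰ = 0.81; 1 − 0.89²⁰ = 0.90.
- At least two (exact binomial): 0.48 to 0.66.

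These figures count photosensitivity reactions of any kind.

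**4. How often both instructions would apply**

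The documents do not say what share of reactions show erythema and are also significant. If half did (an assumption), the rate would be 4 to 5.5%:

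- At least one: 1 − 0.96²⁰ = 0.56; 1 − 0.945²⁰ = 0.68.

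A smaller share lowers this further: at a rate of 2%, 1 − 0.98²⁰ = 0.33.

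**The case against.** The strongest reply is that the texts do not have equal standing. The Special warnings section reads as product information: it uses the brand name and runs on to matters such as infants' fontanelles. The skin entry is a summary of reported effects and says what *should* happen. The management section is the one that sets out steps and says what *will* happen. On this view there is one trial procedure plus background, and to discontinue is simply the stop that the management paragraph then details.

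Part of this stands. The Special warnings text is probably background, and the point does not depend on it. But the skin entry sits among statements specific to this trial, such as the advice patients will be given and the exclusion of oral contraceptive users. The protocol nowhere says that discontinuing means a temporary stop. Even if it did, the triggers would still differ.

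It is also fair that all patients are evaluated at one centre (Study setting), which limits variation in practice.

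Four stronger readings are tempting, and the documents do not support them:

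- *The milder sign carries the firmer consequence.* This holds only if discontinuation is permanent, which the skin entry does not say.
- *The conflict will very probably arise.* The 81 to 90% is the chance of any photosensitivity reaction, not of one that meets both triggers.
- *The FEV1 comparison suffers a one-sided loss.* No effect on slope, power or bias has been shown. Stopping drug is not the same as losing FEV1 data.
- *Withdrawing patients from the study contradicts the follow-up plan.* The primary endpoint text provides for measurements to continue, where possible, in patients who withdraw, so it covers these patients.

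**Conclusion.** The inconsistency is real. It concerns both when study drug stops and whether it restarts, and it is a contradiction within the protocol, not a detail that could be left to an analysis plan.

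Its size is modest: perhaps one or two active-arm patients handled inconsistently, with a possible effect on membership of the per-protocol analysis. No damage to the intention-to-treat FEV1 comparison is shown.

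The expected 1.6 to 2.2 reactions assume that the quoted rate applies at this trial's doses and two-year duration and after the sun-protection advice. The chance of at least one also assumes that patients react independently. The rate cannot be checked from the protocol: it is attributed to references numbered 141 to 151, while the reference list ends at 19. The 56 to 68% for an episode meeting both triggers rests on an assumed share of one half.

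**What to change.** Reconcile the photosensitivity statements in Special warnings, Frequent adverse effects (skin) and Management of adverse events (cutaneous) into one study-drug rule with a single trigger and a single action. If any of the text is meant only as product-information background, say so and refer the reader to the governing paragraph. The clinical content of the rule is for the sponsor to decide.

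This costs protocol wording only. It changes no visit, endpoint or sample size, and on this point the provision for continued measurement after withdrawal can stay as it is.

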#### Management of adverse events associated with doxycycline

**Gastrointestinal.** To reduce the risk of oesophagitis enteric-coated capsules will be used and patients will be advised to take doxycycline at meal times with a full glass of water. If these measures are unsuccessful, we will withdraw the drug and ask the patient to be evaluated by a gastroenterologist.

**Cutaneous.** Patients will be advised about the risk of photosensitivity, and to use good sun protection. For patients in whom a significant episode of tetracycline-induced

photosensitivity develops, treatment with doxycycline will be interrupted for a week to allow resolution of the skin reaction. Methods to protect the skin from exposure to light will be discussed with the patient, and doxycycline treatment will be resumed at the same dose. If this is unsuccessful in preventing further photosensitivity reactions, patients will be withdrawn from the study.

**Dental.** For patients in whom tooth discoloration develops, vigorous oral hygiene will be advised, along with regular follow-up with a dental technician for formal cleansing. Patients will be advised not to use chlorhexidine-containing mouthwashes, which can cause tooth discoloration. If this is unsuccessful in resolving tooth discoloration to the patient's satisfaction, the patient will be removed from the study.

**Infectious.** Doxycycline may cause moderate changes in oropharyngeal and colonic microflora. Non-antimicrobial doses of doxycycline do not appear to have an effect on the composition or resistance of faecal or vaginal microflora (167). It is possible that patients may become colonized with doxycycline resistant organisms. For patients in whom any form of yeast infection developed during the course of the study, doxycycline treatment may be interrupted to permit resolution of the infection, along with vigorous hygiene and anti-fungal treatment, followed by resumption of the study medication.

